6.1.2 Infant Subject Study Visit Procedures

6.1.2.1 Visit 1: Delivery – Hospital Follow-up Visit

All procedures, including routine vaccinations that are considered standard of care for the newborn infant may be performed at any study visit which coincides with the usual timing for such procedures. Before any of the following study-specific procedures are performed, informed consent for the infant subject and release of medical records will be reviewed with the maternal subject (i.e., mothers will not be re-consented) or will be obtained from the other parent or guardian if not captured under the institution’s policy.

- If cord blood is not collected at the time of delivery (see delivery procedures for maternal subjects in Section 6.1.1.7), a blood sample from the infant (2 mL by venipuncture preferred; 1 mL by heel stick acceptable) should be obtained within 72 hours of birth for RSV serology. *(Note: Cord blood is markedly preferred and all efforts should be directed to obtaining this specimen. A phlebotomy/heel stick within 72 hours is a fall back procedure only. The volume of a postpartum phlebotomy/heel stick must be accounted for within the phlebotomy limits as per the investigator’s institution, whereas a cord blood sample need not.)*
- The investigator or a trained designee will perform the following procedures: collection of results from the physical exam, weight, length, frontal-occipital circumference (FOC), and APGAR measurements performed following birth and used to assess the overall health of the infant; and documentation of the mode of infant feeding (e.g., exclusively breastfed, exclusively formula fed, breast milk and supplemented with formula, expressed breast milk, wet nurse, receiving solids), if a smoker or one or more children < 5 years of age will reside in the same household, and whether the infant or another child in the household (< 5 years of age) will be/is cared for in a group setting with other children (e.g., daycare) for ≥ 3 days per week.
- Issue a Study Identification Card to parents and/or guardians of each infant that indicates that he/she is part of an investigational vaccine trial and provides the contact number to the investigator and study staff responsible for the study-related follow-up of the infant, along with a list of the signs and symptoms of RSV infection in adults and infants.

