8.6 Maternal/Fetal/Neonatal Adverse Events of Special Interest

[Table 5](#) summarizes and defines a series of maternal, fetal, and neonatal adverse events that are of special interest in the evaluation of maternal immunization strategies. The majority of these events will fulfill one or more of the criteria listed above for SAEs. In the event that one of these events does not meet the criteria for an SAE (e.g., “Small for Gestational Age” might not), it will nonetheless be reported as an SAE using the same reporting requirements as an SAE. The majority of these terms and definitions are derived from the Brighton Collaboration Definitions of Key Terms (WHO meeting July 2014). Investigators should strive to collect the same level of data as for any SAE, and are encouraged to use the exact terms in [Table 5](#) to report events meeting these definitions (see [Table 5](#) footer for exceptions for reporting of neonatal and infant death). Note that the SAE eCRF/eSource will provide a field for designating an SAE report as a Maternal/Fetal/Neonatal Adverse Event of Special Interest (MFNAESI). Some MFNAESIs are open to interpretation as to which subject should be recorded as sustaining the event. [Table 5](#) also designates to which subject each class of event should be assigned; solely as a uniform data collection convention. Since there are multiple potential sources to determine the GA at birth, the study defined EDD and the birth date will be used to determine the

gestational age (GA) at birth for the summary of the preterm birth categories (Very preterm and Moderate to late preterm).

Table 5: Maternal/Fetal/Neonatal Adverse Events of Special Interest

Term	Definition	Reported as an Event In
Stillbirth:	Delivery of a dead fetus of > 22 weeks gestation, subcategorized as: 
 • Antepartum • Intrapartum 	Mother
Placental Abruption:	Placental separation from the uterus with bleeding (concealed or vaginal) before fetal birth, with or without maternal/fetal compromise	Mother
Preterm Birth:	Delivery of a live newborn child, subcategorized as: 
 • Very preterm: 28 to < 32 weeks gestation • Moderate to late preterm: 32 to < 37 weeks gestation 	Mother

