10.3 Demographics and Protocol Compliance

Demographic parameters and other baseline characteristics (e.g., age, age group, gender, race, ethnicity, etc.) will be summarized by treatment group and serology cohort (as applicable) for all maternal and infant subjects (separately) in the Safety Population, as well as the number and description of protocol deviations. Summary statistics at birth for infant length, weight, FOC, APGAR scores, and gestational age will be provided by treatment groups. In addition, a listing will be prepared linking, by mother/infant pair, maternal demographic characteristics, maternal treatment, and infant length, weight, FOC, APGAR scores, and gestational age at birth.

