4.3. Safety Endpoints

4.3.1. In All Infant Subjects

- Percentages of term (≥ 37 weeks gestational age), healthy infants appropriate for gestational age (as determined by ultrasound gestational age assessment), APGAR scores, length, birth weight, frontal-occipital head circumference (FOC), and physical examination at birth.
- Percentages of infants with AEs and SAEs (with special attention to congenital anomalies, respiratory failure other than RSV-associated hospitalization; neonatal death; infant death; sudden infant death syndrome; asphyxia; neonatal or hypoxic-ischemic encephalopathy; or other adverse events or complications of adverse events that necessitate hospitalization) during the neonatal period and through the first year of life.
- Percentages of infants with unsolicited adverse events (including abnormalities detected in routine metabolic screening blood and neonatal hearing tests), unscheduled medical visits for adverse events, and serious adverse events through the first year of life.
- Percentages of infants with developmental delay, as measured by the outcome of testing using a validated developmental scale at six months and at one year, in infants of RSV F vaccinees as compared to placebo.

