7. DEMOGRAPHICS AND OTHER BASELINE CHARACTERISTICS

Demographic parameters and other baseline characteristics (age at Day 0 vaccination, gender [for infants], ethnicity, race, height [cm], weight [kg]) will be summarized by treatment group and serology cohort (as applicable) for all maternal and infant subjects (separately) in the Safety Population. Descriptive statistics (number of subjects [N], mean, median, minimum and maximum values) will be presented for weight (kg), and height (cm) measurements recorded at Study Day 0. No statistical testing will be performed on these data.

Age (years) at the Day 0 vaccination will be calculated as the closest lower integer result of (date of Study Day 0 vaccination – date of birth) / 365.25, and will be presented as a continuous variable, using descriptive statistics. Age will also be summarized as a categorical variable (e.g., 18 to < 29 years and 29 to \leq 40 years). Gender of infants will be summarized as a categorical variable (e.g., “Male”, “Female”). Ethnicity will be summarized as number and percentage of subjects according to predefined categories (i.e., Hispanic or Latino, not Hispanic or Latino) listed in the eCRF. Race will also be summarized as number and percentage of subjects according to predefined categories (i.e., American Indian or Alaska Native, Asian, Black or African American, Native Hawaiian or Other Pacific Islander, and White).

Continuous variables will be presented by summary statistics (e.g., mean and standard deviation for the non-immunogenicity endpoints, and geometric means and their 95% confidence intervals for the immunogenicity endpoints); APGAR scores and other infant health outcomes at delivery may additionally be summarized as medians and interquartile ranges. Categorical variables will be presented by frequency distributions (frequency percentages for the non-immunogenicity endpoints, and percentages and their 95% confidence intervals for the immunogenicity endpoints).

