12.1. Overall Handling of Adverse Events

The principal variable for evaluation of the safety profile for the RSV F vaccine will be the number and percentage (95% CI) of maternal subjects with solicited and unsolicited adverse events (including MAEs and SAEs) recorded post-vaccination, and the number and percentage (95% CI) of infants with unsolicited AEs occurring since birth. An overall summary will present the number and percentage of solicited adverse events in maternal subjects by verbatim term and treatment group; and unsolicited adverse events by MedDRA SOC and PT, and by treatment group for all maternal and infant subjects in the Safety Population. Laboratory values and vital signs will also be summarized (percentages) by treatment group for all maternal subjects in the Safety Population.

Solicited adverse events occurring in the first 7 days after each dose of test article will be presumed to be related; and severity will be graded by specific definitions included in the protocol and subject diary. Unsolicited adverse event summaries by relationship to study vaccine will be categorized as “not related” (including “unrelated or unlikely”) or “related” (including “possible, probable, and definite”). For multiple occurrences of an adverse event in the same subject, a subject will be counted only once, using the most severe or most related occurrence for the summarization by severity or relationship to study vaccine, respectively.

Solicited adverse events will not be coded, and will be summarized by solicited term only. All unsolicited adverse events will be coded using MedDRA version 16.1.

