12.2. Analyses of Safety Objectives

Safety will be summarized for maternal and infant subjects separately. Safety will be summarized overall and by treatment group for maternal and infant subjects based on percentages.

Tabulations of counts and proportions of the following safety parameters, by treatment group and overall, will be produced for maternal subjects:

- Solicited seven-day reactogenicity events by severity;
- Clinical laboratory safety abnormalities by severity;
- Caesarean, vaginal, and instrument-assisted vaginal modes of delivery;
- Pre-specified third-trimester pregnancy and delivery complications (i.e., stillbirth, placental abruption, preterm birth, preterm premature rupture of membranes, hypertensive disorders of pregnancy, third-trimester hemorrhage, and gestational diabetes), and labor and delivery complications (i.e., emergency Caesarean section, postpartum hemorrhage, chorioamnionitis, and maternal fever or infection); and
- Unsolicited adverse events through 180 days post-delivery by severity and relatedness (possibly, probably, or definitely), including SAEs, MAEs, and SNMCs.

Tabulations of counts and proportions of the following safety parameters, by treatment group and overall, will be produced for infant subjects:

- Congenital anomalies; respiratory failure other than RSV-associated hospitalization; neonatal death; infant death; sudden infant death syndrome; asphyxia; neonatal or hypoxic-ischemic encephalopathy; or other adverse events or complications of adverse events that necessitate hospitalization during the neonatal period and through the first year of life;
- All other unsolicited/unspecified adverse events by severity, relatedness, and seriousness, including respiratory events that test negative for RSV by RT-PCR.

Summary statistics will also be provided for infant length, weight, FOC, 1- and 5-minute APGAR scores, and responses to environmental and behavioral queries, through one year post-delivery overall, and by treatment group. Results of developmental testing will be summarized by treatment group, and percentages of infants in the developmental testing subset above normal, normal, at-risk at 6 or 12 months, and at-risk at both 6 and 12 months.

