12.6. Maternal/Fetal/Neonatal Adverse Events of Special Interest

Table 2 summarizes and defines a series of maternal/fetal/neonatal adverse events that are of special interest in the evaluation of maternal immunization strategies. The majority of these events will fulfill one or more of the criteria listed below (Section 12.7) for SAEs. In the event that one of these events does not meet the criteria for an SAE (e.g., "Small for Gestational Age" might not), it will nonetheless be reported as an SAE using the same reporting requirements as an SAE. The majority of these terms and definitions are derived from the Brighton Collaboration Definitions of Key Terms (WHO meeting July 2014). Some maternal/fetal/neonatal AESIs are open to interpretation as to which subject should be recorded as sustaining the event. **Table 2** also designates to which subject each class of event should be assigned; solely as a uniform data collection convention. Since there are multiple potential sources to determine the gestational age (GA) at birth, the study defined EDD and the birth date will be used to determine the GA at birth for the summary of the preterm birth categories (Very preterm and Moderate to late preterm).

Table 2: Maternal/Fetal/Neonatal Adverse Events of Special Interest

Term	Definition	Reported as an Event In
Stillbirth:	Delivery of a dead fetus of > 22 weeks gestation, subcategorized as: 
• Antepartum• Intrapartum	Mother
Placental Abruption:	Placental separation from the uterus with bleeding (concealed or vaginal) before fetal birth, with or without maternal/fetal compromise	Mother
Preterm Birth:	Delivery of a live newborn child, subcategorized as: 
• Very preterm: 28 to < 32 weeks gestation• Moderate to late preterm: 32 to < 37 weeks gestation	Mother
Gestational Hypertension/Pre-Eclampsia/Eclampsia:	Gestational Hypertension: New onset elevations of blood pressure after 20 weeks of gestation, in the absence of accompanying proteinuria. Pre-Eclampsia: A hypertensive disorder of pregnancy with: 
• A blood pressure $\geq 140/\geq 90$ on 2 occasions, at least 4 hours apart after 20 weeks of gestation, or a blood pressure $\geq 160/\geq 110$ and the presence of	Mother

Table 2: Maternal/Fetal/Neonatal Adverse Events of Special Interest

Term	Definition	Reported as an Event In

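### The percentage of term, healthy infants appropriate for gestational age is a stated safety endpoint, but no planned output gives it

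*SAP*

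**What the plan says.** **The endpoint.** SAP 4.3.1 and Protocol 3.2.4.1 both open the infant safety endpoints with a percentage of term, "healthy infants appropriate for gestational age (as determined by ultrasound gestational age assessment"), followed by the birth measurements.

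**Collection.** Protocol 6.1.2.1 requires, at the delivery visit, "collection of results from the physical exam, weight, length, frontal-occipital circumference (FOC), and APGAR measurements performed following birth". Infant sex is recorded (SAP 7). Gestational age at birth follows from the study due date and the birth date (SAP 12.6).

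**Planned summaries of birth size.** SAP 12.2: "Summary statistics will also be provided for infant length, weight, FOC, 1- and 5-minute APGAR scores, and responses to environmental and behavioral queries". Protocol 10.3: "Summary statistics at birth for infant length, weight, FOC, APGAR scores, and gestational age will be provided by treatment groups", plus a mother–infant listing. SAP 7 adds that "APGAR scores and other infant health outcomes at delivery may additionally be summarized as medians and interquartile ranges".

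**SGA and low birth weight.** Both are defined in the tables of special-interest events (SAP Table 2, Protocol Table 5). If such an event is not otherwise serious, "it will nonetheless be reported as an SAE using the same reporting requirements as an SAE". Protocol 8.6: "Note that the SAE eCRF/eSource will provide a field for designating an SAE report as a Maternal/Fetal/Neonatal Adverse Event of Special Interest". They reach a comparison by arm through the general tables, which present "unsolicited adverse events by MedDRA SOC and PT, and by treatment group for all maternal and infant subjects in the Safety Population" (SAP 12.1).

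**The concern.** A percentage of AGA infants needs a joint classification of weight, gestational age and sex. Separate summaries of weight and of gestational age cannot supply it, because the same two marginal distributions are compatible with different proportions of small infants. A count of reported SGA events cannot supply it either. AGA is not the complement of reported SGA, since infants whose SGA was never reported, and infants large for gestational age, would both be left in the remainder.

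The vaccine is given to healthy women in the third trimester, and fetal growth is one of the listed infant safety outcomes. As written, one part of a stated endpoint would be absent from the report, or would be built later with a definition and reference chosen after the treatment codes are known.

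**Working it through.** The plan gives no figure for this endpoint, so there is none to reproduce. The check sets the endpoint against each planned output.

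| Planned output | What it gives | Gives % AGA? |
|---|---|---|
| SAP 12.2, infant tabulations | Named events (congenital anomalies, deaths, asphyxia and so on) and all other unsolicited events; AGA, SGA and low birth weight not named | No |
| SAP 12.2, summary statistics | Length, weight, head circumference and APGAR, each separately | No |
| SAP 7 | Demographics; optional medians and interquartile ranges for delivery outcomes | No |
| Protocol 10.3 | Weight and gestational age by arm, separately; a listing that pairs them | No |
| Protocol 10.6 | Essentially the same content as SAP 12.2 | No |
| SAP 12.1, 12.4, 12.7 | Reported adverse events by preferred term and arm; a listing of serious events | Reported SGA and low birth weight only |
| SAP 12.6 | Definitions; gestational age derived for the preterm categories | Term status only |

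The term part is therefore covered. The AGA part is not, and neither document says what makes an infant healthy for this purpose. Low birth weight has fixed gram limits and needs no reference. SGA is defined relative to the same population, and no reference is named. Neither document states an upper limit for AGA.

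**Scale (illustration).** Inputs are the target maternal group sizes in SAP Table 1, 1,562 placebo and 3,038 vaccine. I assume one live-born infant per mother; pregnancies are singleton. All event rates and reporting fractions below are assumptions.

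*Precision of a derived percentage.* The 95% half-width for the difference between arms is 1.96·√[p(1−p)(1/1562 + 1/3038)] = 0.0610·√[p(1−p)].
- Term-and-AGA at 75, 80, 85 or 90%: 2.6, 2.4, 2.2 or 1.8 points.
- SGA or low birth weight at 2, 5 or 10%: 0.9, 1.3 or 1.8 points.

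*Effect of incomplete reporting.* Suppose sites report a fraction f of true SGA cases, equally in both arms, and the true risk ratio is 1. Then q = p·f, the number unreported is 4,600·p·(1−f), and the 95% interval is exp{±1.96·√[(1−q)/(1562q) + (1−q)/(3038q)]}.

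| f | Unreported, p = 10% (of 460) | 95% CI | Unreported, p = 5% (of 230) | 95% CI |
|---|---|---|---|---|
| 100% | 0 | 0.83–1.20 | 0 | 0.77–1.30 |
| 90% | 46 | 0.82–1.21 | 23 | 0.75–1.32 |
| 70% | 138 | 0.80–1.25 | 69 | 0.73–1.38 |
| 50% | 230 | 0.77–1.30 | 115 | 0.68–1.46 |

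With near-complete reporting the loss of precision is small. The missing AGA percentage does not depend on f.

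**The case against.** **General commitments to report.** The protocol synopsis says that safety endpoints will be summarised by arm, and SAP 12.2 opens by saying that safety will be summarised by percentages. This does not close the gap. The synopsis sentence is tied to subjects with an adverse event, and the SAP sentence supplies no AGA variable, cut-off or reference.

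**Documents not supplied.** Table shells, the eCRF and the operations manual might contain an AGA table, or might derive low birth weight from the gram limits in SAP Table 2. That cannot be excluded. Neither supplied document refers to such a table, however, and the definition and reference belong in the SAP.

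**The preterm comparison.** The SAP gives its derivation of gestational age because several sources may conflict, and no such conflict is stated for birth weight. That is a fair distinction. The preterm rule is a model for the derivation rather than proof that one was overlooked.

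**Growth is already compared.** Birth weight, length, head circumference and gestational age are summarised by arm, and SGA and low birth weight are mandatory, flagged reports. This stands. A reader might infer that fetal growth goes unexamined or that SGA is never compared by arm, and the documents do not support that.

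**The reference.** Defining SGA against the same population suits a multinational trial, and a single chart would depart from it. This also stands, and it is a reason to allow country references.

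**Conclusion.** The concern holds in a limited form: the plan states a percentage of term, healthy, AGA infants and contains no output that gives it. That rests on the text of the two documents alone. Deriving low birth weight, SGA and AGA from recorded data would replace counts of reports with complete ascertainment wherever weight, sex and gestational age are known. The change should be made, but the endpoint is descriptive and the consequence is modest.

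Two stronger readings are not supported. The first is that reliance on site reports biases the comparison or hides a growth signal. No document gives a reporting rate, clinical site staff are blinded to treatment (Protocol 3.6), and the reporting fractions above are assumed, so they show possible loss of precision only. The second is that the difference between SAP Table 2, which equates SGA with intrauterine growth restriction, and Protocol Table 5, which separates them, corrupts the counts. Sites report under the protocol's definitions and events are tabulated by preferred term, so this is a wording correction. Nothing here bears on the efficacy conclusions.

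**What to change.** In SAP 12.2, for every infant in the Safety-I population with a recorded birth weight:

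1. Derive the <2,500 g, <1,500 g and <1,000 g categories from the measured weight.
2. Derive SGA (below the 10th percentile) and AGA from measured weight, sex and gestational age by the study due date, using the SAP 16.6 fallback if that date is missing. State the upper limit of AGA, for example the 10th to 90th percentile, with large-for-gestational-age infants shown separately. Name the reference, or one reference per country, before unblinding.
3. Tabulate the percentages with low birth weight, with SGA, and both term and AGA, by arm with 95% confidence intervals, beside the site-reported events.
4. Either define healthy, or state that the tabulated percentage covers term and AGA only.
5. List intrauterine growth restriction separately from SGA in SAP Table 2, as Protocol Table 5 does.

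The cost is SAP wording and one or two tables from data already collected, plus the choice of reference. A single reference departs from the same-population wording, equally in both arms. Country references keep to that wording but need more than one chart.

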12.3. Solicited Adverse Events

Solicited AEs for maternal subjects are pre-specified in Section 8.2.1 of the protocol and include both injection site reactions (i.e., pain, bruising, redness, and swelling) and systemic events

(i.e., oral temperature [for assessment of fever], chills, muscle pain, joint pain, diarrhea, nausea, vomiting, headache, and fatigue) that are reported within seven days following the Day 0 vaccination and are solicited by diary. These events are considered related to the study vaccine and are collected using a severity rating of 0 (did not occur), or 1, 2, or 3 (mild, moderate, or severe, respectively), using the maximal severity observed for the specific symptom post-vaccination. Notable exceptions include temperature, which is collected as a continuous variable, and that uses temperature grade ranges established in the toxicity grading scale (TGS), which are applied later in the analysis, and events of injection site redness and swelling, which will be measured using a Subject Measurement Tool (see protocol, [Appendix 4](#)). The Subject Measurement Tool is a transparent acetate sheet imprinted with a set of concentric circles with diameters that correspond to TGS ranges that are also used to assign severity.

Solicited AEs will be tabulated and analyzed by the verbatim terms specified in the diary, and not MedDRA coded. Analysis will use exact diary wording (i.e., “muscle pain” rather than changing it to “myalgia”). Only solicited adverse events which record a start date within the 7-day window of the Day 0 to Day 6 post-vaccination period will be included in the tabular summary and listing of solicited events. Solicited AEs will be presented by treatment group for all maternal subjects.

Solicited AEs, collected from the subject diary, which continue after the collection period (i.e., post-vaccination Day 6) will be captured by verbatim term, on an AE electronic case report form (eCRF) page and flagged in the listing of solicited AEs.

The following summaries of solicited AEs will be presented by treatment group as part of the secondary analysis of safety:

- Summary of solicited treatment-emergent AEs by the verbatim terms specified in the diary and within the post-vaccination window (Days 0 - 6).
- A summary of all solicited AEs by severity (mild, moderate, severe), and within the post-vaccination window (Days 0 - 6).

